ANCOVA	Analysis of Covariance
CFR	Code of Federal Regulations
CLIA	Clinical Laboratory Improvement Amendments
MP	Monitoring Plan
COC	Certificate of Confidentiality
CONSORT	Consolidated Standards of Reporting Trials
CRF	Case Report Form
DCC	Data Coordinating Center
DHHS	Department of Health and Human Services
DSMB	Data Safety Monitoring Board
DRE	Disease-Related Event
EC	Ethics Committee
eCRF	Electronic Case Report Forms
FDA	Food and Drug Administration
FDAAA	Food and Drug Administration Amendments Act of 2007
FFR	Federal Financial Report
GCP	Good Clinical Practice
GLP	Good Laboratory Practices
GMP	Good Manufacturing Practices
GWAS	Genome-Wide Association Studies
HIPAA	Health Insurance Portability and Accountability Act
IB	Investigator's Brochure
ICH	International Conference on Harmonization
ICMJE	International Committee of Medical Journal Editors
IDE	Investigational Device Exemption
IND	Investigational New Drug Application
IRB	Institutional Review Board
ISM	Independent Safety Monitor
ISO	International Organization for Standardization
ITT	Intention-To-Treat

[MagPro X100 Stimulator, Cool-B65 Butterfly Coil]

Page 7 of 39

LSMEANS	Least-Squares Means
MedDRA	Medical Dictionary for Regulatory Activities
MOP	Manual of Procedures
MSDS	Material Safety Data Sheet
NCT	National Clinical Trial
NIH	National Institutes of Health
NIH IC	NIH Institute or Center
OHRP	Office for Human Research Protections
PI	Principal Investigator
QA	Quality Assurance
QC	Quality Control
SAE	Serious Adverse Event
SAP	Statistical Analysis Plan
DSMC	Data Safety Monitoring Committee
SoA	Schedule of Activities
SOC	System Organ Class
SOP	Standard Operating Procedure
UADE	Unanticipated Adverse Device Effect
UP	Unanticipated Problem
US	United States

[MagPro X100 Stimulator, Cool-B65 Butterfly Coil]

Page 8 of 39

1 STUDY SUMMARY

1.1 Synopsis

Title: [Intensive TMS for Rapid Relief of Bipolar Depression Symptoms]

Short Title: [Intensive TMS for Bipolar Depression]

Study Description:

[The research study is being conducted to test whether using high dose spaced theta-burst rTMS (a form of transcranial magnetic stimulation) produces a significant reduction in depressive symptoms compared with sham. This project will recruit patients aged 18-70 with symptoms of bipolar depression who have failed (or not shown signs of improvement) after at least two prior treatments. The null hypothesis is that there will be no difference in reductions in depressive symptoms by the end of a five-day treatment period. The alternative hypothesis is that, compared with sham, active TMS will result in a greater reduction in depressive symptoms by the end of the treatment period.]

Objectives:

[The overall objective of this project is to test whether using high dose spaced theta-burst rTMS (HDS-TBS) produces a significant reduction in depressive symptoms compared with sham.]

Primary Endpoint:

[Aim 1: To assess clinical efficacy of HDS-TBS.]

Secondary Endpoints:

Population:

[Aim 2: To determine the effect of iTBS on DLPFC rsfMRI and establish

a relationship between change in brain resting state functional

connectivity and treatment effects.]

Study

[34 subjects (with 32 usable data), within the ages of 18-70, right or left handed, gender inclusive, diagnosed with Bipolar I & II depressed (per

DSM 5 criteria)]

Phase: [N/A]

Description of

[Center of Neuromodulation in Depression & Stress, University of

Sites/Facilities Pennsylvania]

[MagPro X100 Stimulator, Cool-B65 Butterfly Coil]

Page 9 of 39

Enrolling Sites: [Center of Neuromodulation in Depression & Stress, University of

Pennsylvania]

Description of

Study Intervention:

[Intensive iTBS. This includes intermittent theta-burst stimulation (iTBS), a patterned form of repetitive transcranial magnetic stimulation (rTMS)

over the left dorsal lateral prefrontal cortex (L-DLPFC).]

Study Duration: [1 year]

Participant Duration:

[figure not shown]
[6-8 weeks]

1.3 Schema

[MagPro X100 Stimulator, Cool-B65 Butterfly Coil]

Page 11 of 39

2 INTRODUCTION AND RATIONALE

2.1 Study Rationale

[Bipolar disorder (BD) is prevalent, severe and under studied, and is often excluded from clinical trials. The depressive phase of illness accounts for the majority of time ill: 72% in BD-I and 81% in BD-II [1]. Many patients fail to respond adequately or cannot tolerate pharmacotherapy due to side effects. Thus alternative treatment options are important to help achieve and sustain remission.

One option, transcranial magnetic stimulation, (TMS) is a relatively new non-invasive approach that involves modulating brain networks with magnetic pulses applied to the skull surface. To date, the best evidence for TMS efficacy has been demonstrated in treatment resistant major depression, although there have been a small number of studies finding treatment response in BD [2] High dose spaced theta burst TMS (HDS-TBS) is among recent emerging technologies for rapid reduction of depressive symptoms.]

2.2 Background

[Li et al [3] first described the efficacy of a course of intermittent theta-burst stimulation (iTBS), a patterned form of repetitive transcranial magnetic stimulation (rTMS) over the left dorsal lateral prefrontal cortex (L-DLPFC) in patients with treatment refractory depression. In that study the degree of refractoriness was predictive of reduced efficacy, suggesting that highly refractory patients may require more TMS pulses to produce an antidepressant response. TBS has been shown to be more efficient than standard rTMS in modulating cortical excitability and multiple spaced iTBS (intermittent theta burst stimulation) sessions can be used to accelerate the treatment response. Recent work with transcranial magnetic stimulation (TMS) has shown that a rapid and sustained treatment response can be achieved by concentrating the usual 4-6 weeks of daily treatment into a high dose spaced theta burst TMS (HDS-TBS) treatment for 5 days [4]. Patients in that study were required to have failed conventional rTMS treatment and to meet deep brain stimulation inclusion criteria. However, that study only included MDD and excluded bipolar disorder. To date, there are no studies of HDS-TBS in bipolar disorder.

To demonstrate the feasibility of administering a high dose TBS protocol in our Center we recruited six patients with MDD into a pilot study using HDS-TBS according to the same parameters as will be used in the current proposal (10 treatments/day x 5 days), with the same stimulation settings. In our pilot study (IRB Protocol #834723), however, we only included participants with a diagnosis of MDD. Following treatment, patients had a mean reduction of 38.6% in depressive symptoms on the MADRS.]

2.2.1 Pharmacokinetics, Pharmacodynamics and Toxicology

[N/A]

[MagPro X100 Stimulator, Cool-B65 Butterfly Coil]

Page 12 of 39

2.2.2 Assessment for Potential Study Products Drug-Drug, Drug-Device, Device-Device Interactions

[No other drugs or devices are included in this trial, besides the TMS system.]

2.2.3 Clinical Adverse Event Profile

[Common mild AEs from TMS include: headache, local pain and discomfort, dizziness/nausea. Rare severe AEs from TMS include: seizures, worsening of depression, hearing loss, burns form the coil.

Other AEs include emotional discomfort during assessments, physical discomfort with MRI, anxiety or claustrophobia during MRI, worsening of depressive symptoms over time, mania symptoms and suicidality. In rare instances, severe AEs from MRI can include injury.]

2.2.4 Dosing Rationale

[MagVenture TMS Therapy System with Theta Burst Stimulation is FDA approved.]

2.3 Risk/Benefit Assessment

2.3.1 Known Potential Risks

[iTBS &TMS. This study utilizes two forms of Transcranial Magnetic Stimulation (TMS): intermittent Theta Burst Stimulation (iTBS) & single pulse TMS. TMS is a FDA-approved non-invasive brain stimulation technique for a variety of diagnoses. iTBS was recently approved by the FDA to be used to treat depression as well. As with any technique, there may be long-term risks due to TMS that are currently unknown. The most common side effect of TMS (approximately 25% of subject) is a mild headache. There are no known long-term adverse effects reported with the use of this device. Rarely, device malfunction could result in a scalp burn (less than 1% of subjects).

- Certain Medical Diagnoses: For subjects with epilepsy, activation of the brain by TMS could also activate a seizure. Subjects with stroke may be at increased risk for a seizure due to the brain scar, therefore, those with history of epilepsy or stroke will be excluded from the study. For a typical physically healthy person, a TMS-induced seizure in this experiment is very unlikely.
- **Noise**: The TMS device produces a clicking sound. To minimize this possibility, you will be given protective earplugs or headphones.
- Nausea: Although it is uncommon, approximately 5% of subjects have experienced nausea during the experiment. You can discontinue the experiment if you experience any discomfort during the study.
- **Mild Swelling or Bruising**: You may also experience temporary and local bruising, swelling, or pain from the swim cap and/or muscle activation by TMS.

[MagPro X100 Stimulator, Cool-B65 Butterfly Coil]

Page 13 of 39

Accelerated iTBS. Present research about increased iTBS frequency [3, 4] does not suggest any increased risk of side effects due to the increased treatment frequency. Current research also showed no significant difference between accelerated and conventional TMS treatment schedules [5] That being said, patients will be monitored for worsening of depressive symptoms or side effects. If patients experience worsening of depressive symptoms (i.e. increased insomnia, increased negative thoughts, increased suicidality), they will be referred to the study physician and/or to research study staff for evaluation and possible next steps.

Clinical assessments and self-report questionnaires. Some discomfort may be associated with the clinical assessments conducted in this study. Patients may experience emotional discomfort when answering some questions in the questionnaires or when talking about personal information. They may choose not to answer any of the questions and to terminate study participation.

MRI Scan.

- Claustrophobia: Patients may experience claustrophobia (fear of enclosed spaces and/or anxious feelings accompanied by fast heart rate or shortness of breath) within the MRI scanner. An MRI scan requires participants to be in a partially enclosed space inside the scanner. Some people may find this to be uncomfortable and claustrophobic. Patients need to inform the doctor ordering the scan, or the study staff, if they suffer from claustrophobia.
- Magnetic Fields: There is no known health risk associated with exposure to magnetic fields during an MRI. There are minimal risks from the loud noise associated with the MRI scanner and from the discomfort of lying on a hard surface. We shall provide protective earplugs as necessary and make every attempt to ensure comfort with blankets, etc. during time in the scanner.
- Flying Objects: The greatest risk of MRI is a magnetic object flying through the air toward the magnet and hitting you. To reduce this risk we require that all people involved with the study remove all magnetic metal from their clothing and all magnetic metal objects from their pockets. No magnetic metal objects are allowed to be brought into the magnet room at any time except by approved personnel. In addition, once in the magnet, the door to the room will be closed so that no one inadvertently walks into the room.
- Medical Implants and Foreign Bodies: There is also a potential risk of MRI for subjects with medical implants or other metallic objects in their body. All subjects undergoing MRI scanning must complete a screening evaluation risk in advance of the study for the presence of medical implants or other foreign bodies that could pose an injury. Every effort will be made to insure that disclosed implants or foreign bodies do not pose a risk to subjects. In cases where there is insufficient information to evaluate the risks associated with an implant or foreign body, the MRI study will not be allowed to proceed.

[MagPro X100 Stimulator, Cool-B65 Butterfly Coil]

Page 14 of 39

- **Pregnancy**: Although there are no known risks related to MRI on pregnant women or a fetus, there is a possibility of yet undiscovered pregnancy related risks. Since there is no possible benefit from participating in this protocol for a pregnant woman, we will exclude pregnant women.
- Incidental Findings Clause: This MRI is not a clinical scan. It is possible that during the course of the research study, the research staff may notice an unexpected finding(s). Should this occur, the finding(s) will be considered by the appropriate personnel and the PI will inform patients if necessary. These possible finding(s) may or may not be significant and may lead to anxiety about their condition and to further work-up by outside physician.

Worsening of Depression Symptoms. While participating in this study, symptoms worsen to the point where of needing psychological or medical support, patients will be given resources to emergency services. If a patient's symptoms require urgent attention, they will be informed to call 911 and present to the nearest emergency room or contact: Philadelphia Behavioral Health at [contact]. PBH hotlines are staffed 24 hours a day, 7 days per week. For similar hotlines outside of the Philadelphia area, they can consult www.suicide.org.

Risk to confidentiality. There is a rare risk that confidentiality could be breached in this study. Breaches in confidentiality could impact future insurability and/or employability.

[name] will provide clinical monitoring as needed. He will act as clinical and safety monitor and ensure compliance.]

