2.3.3 Assessment of Potential Risks and Benefits

[The risks associated with this study are no greater than those encountered in standard clinical treatment with Transcranial Magnetic Stimulation (TMS). The aspects of this study that are implemented for the purposes of the study alone (the MRI scan and assessments of symptoms) are minimal risk. Participants who have an obvious contraindication to TMS or MRI in their medical record will not be presented in this study; those who consent will be asked to complete an MR-safety form upon consent. Should any MRI contraindications be discovered at this time, they will not be enrolled in the study.

The potential benefit to patients (e.g., reduced time burden) and medical community through the increased understanding of this treatment method for individuals with depression, far outweighs the potential risk from the MRI and TMS procedures.]

[MagPro X100 Stimulator, Cool-B65 Butterfly Coil]

Page 15 of 39

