5.2 Exclusion Criteria

[An individual who meets any of the following criteria will be excluded from participation in this study:

- No current substance abuse disorder for the past 6 months (previous substance abuse not exclusionary)
- Any psychotic disorder or current active psychotic symptoms (personality disorders not exclusionary unless in the opinion of the referring psychiatrist it would jeopardize participation)
- No dementia or other major neurological disorders
- Not having depression as primary disorder
- No major medical illness, for example metastatic cancer, end stage renal disease
- Not able to verify contact information. Participants must be able to follow through with the study & must have verified contact information and at least one verified contact
- Pregnancy. While there are no known risks to a fetus this is a new use of TMS, which has not been tested, thus pregnancy is exclusionary
- Score on YMRS greater than 12 (patients with mixed features have been shown not to respond well to TMS treatment [10])
- Rapid cycling Bipolar illness (patients with > 4 mood episodes within the past year will be excluded, as they have a higher risk of switch to mania [11])

[MagPro X100 Stimulator, Cool-B65 Butterfly Coil]

Page 20 of 39

- Any implants, conditions, or contraindications that would be deemed unsafe for TMS or MRI
- Currently using benzodiazepines (such as lorazepam) with a dose >1 mg per day or equivalent]

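### Section 2.3.1 excludes anyone with a history of epilepsy or stroke, but the exclusion list in 5.2 names neither, and three of its bullets are worded in reverse

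*Combined protocol and SAP*

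**What the plan says.** Section 2.3.1 (Known Potential Risks) explains that TMS could provoke a seizure in people with epilepsy and that stroke may raise the risk, and concludes: "therefore, those with history of epilepsy or stroke will be excluded from the study". The rule is categorical and refers to history, not only to current disease.

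Section 5.2 (Exclusion Criteria) opens with "An individual who meets any of the following criteria will be excluded from participation in this study". Its eleven bullets contain no reference to epilepsy, seizure or stroke, and the inclusion list in 5.1 has none either. The bullets that bear on the point are:

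- the neurological bullet: "No dementia or other major neurological disorders";
- the general safety bullet, second to last in the list: "Any implants, conditions, or contraindications that would be deemed unsafe for TMS or MRI".

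Two further bullets share the negative phrasing of the neurological one: "No current substance abuse disorder for the past 6 months" and "No major medical illness, for example metastatic cancer, end stage renal disease".

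Other sections describe screening for TMS safety. Section 2.3.3 says "Participants who have an obvious contraindication to TMS or MRI in their medical record will not be presented in this study". Section 8.2 plans safety screening for both MRI and TMS, and 8.3.10 refers to a TMS safety screening form in connection with pregnancy. The form's items are not given.

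**The concern.** Sections 5.5 and 6.3 make the inclusion and exclusion criteria the test for being invited to screening and for being randomized. A rule that stands only in the risk narrative is easily missed at both steps. The population that the risk assessment describes is then not quite the population that the criteria define.

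This matters here because section 2.2.3 lists seizure among the rare severe adverse events of TMS, section 9.4.4 plans no safety analysis, and section 10.1.5 leaves ongoing safety monitoring with the PI. Screening is therefore one of the main protections against this event, and the operative list should say what the risk section says.

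The reversed bullets are a lesser matter of drafting, but one of the three is the neurological bullet on which the exclusion would otherwise partly rest.

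**Working it through.** No figure in the plan bears on this point, so there is nothing to recompute. The check is a comparison of texts.

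**Step 1: is the rule in 2.3.1 carried into the lists?** No. Neither 5.1 nor 5.2 names epilepsy, seizure or stroke. The pregnancy rule is a useful contrast. Section 2.3.1 also says that pregnant women will be excluded, and 5.2 repeats this as its own bullet. The epilepsy and stroke rule was not treated in the same way.

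**Step 2: do other bullets in 5.2 give the same result?** The cases below are illustrations, not patients described in the documents. The neurological bullet is read as it was evidently meant.

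| Candidate | Section 2.3.1 | 5.2, neurological bullet | 5.2, general safety bullet |
|---|---|---|---|
| Current epilepsy | Excluded | Very probably excluded | Excluded if judged unsafe |
| Past epilepsy, no longer active | Excluded | Open: the bullet is silent on history | Depends on judgement |
| Old stroke with recovery | Excluded | Open: the bullet is silent on history | Depends on judgement |

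The two sections probably agree on current disease. They can diverge on history, which 2.3.1 covers expressly.

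**Step 3: does screening outside 5.2 close the gap?** It may, but the documents do not show it.

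- The record check in 2.3.3 catches only obvious contraindications. Section 5.5 also lets patients make contact themselves and be screened by phone or self-report.
- The TMS screening in 8.2 and the form in 8.3.10 exist, but no epilepsy or stroke item is described.
- The Schedule of Activities (12.1) has a medical history row at screening and no row for TMS safety screening.

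**Step 4: direction of wording in 5.2.** The lead-in excludes whoever meets a bullet. The bullets on substance abuse, on dementia and neurological disorders, and on major medical illness each begin with a negation, so a literal reader would exclude people without the condition. That is three of eleven. Two other bullets also open with a negation (depression not being the primary disorder, and contact details that cannot be verified), but these run in the right direction.

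**Step 5: the substance bullet.** It joins a current disorder to a six-month window and adds that earlier abuse does not exclude. A candidate whose disorder ended three months ago could be read as eligible or as excluded.

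**The case against.** The strongest reply is that nothing in 5.2 contradicts 2.3.1; it is only less specific. Section 2.3.1 is current protocol text, so enrolling a person whom it excludes would be a departure from the protocol, and section 10.1.9 asks the team to document every such departure, not only breaches of 5.2. Section 5.2 also has a correctly worded bullet on conditions unsafe for TMS, and 2.3.1 itself links epilepsy and stroke to seizure risk, so the protocol has largely made that judgement already. A record check, a TMS safety screening and a medical history stand behind it.

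Much of this stands, and it rules out two stronger readings. A reader might infer that the exclusion cannot be enforced at all, or that a site could admit such a patient with no deviation to record. The documents support neither: there are routes to exclusion, and the deviation section covers the whole protocol. What remains is that those routes rest on judgement and on a form whose content is not shown, whereas the rule in 2.3.1 leaves no discretion. Staff working from 5.2 might not recognise that a departure had occurred.

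It is also fair to say that nobody would apply the reversed bullets literally. Sections 4.1, 8.1 and 8.2 screen for dementia with the MMSE, which confirms the intent of that bullet. This part of the point is about clear drafting and does not suggest that the wrong patients would be enrolled.

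**Conclusion.** The point holds as a mismatch between the risk section and the operative eligibility list. A categorical, history-based exclusion in 2.3.1 is absent from 5.2, and the cover that remains is discretionary or not shown. The three reversed bullets are a drafting fault with clear intent.

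The size cannot be put in numbers: the documents do not say how many candidates have past epilepsy or an earlier stroke, nor what the TMS safety form asks. If the form already has explicit items on both, the practical gap is small and only the text needs repair. If it does not, the outcome for such a candidate depends on the individual assessor.

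A reader might also infer that 2.3.1 rests its statement about a seizure being very unlikely on this exclusion. The text does not say so; that statement is limited to a typical physically healthy person and is not given as a consequence of the exclusion.

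The sample size and the primary analysis are unaffected.

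**What to change.** 1. Reconcile 2.3.1 and 5.2 so that the same rule on epilepsy and stroke, including how history is treated, appears in both.
2. Confirm that the existing TMS safety screening form covers that rule.
3. Reword the three negative bullets (substance abuse, dementia and neurological disorders, major medical illness) as positive exclusions, keeping their present examples.
4. Have the sponsor state whether the substance bullet means a current disorder only or any disorder within the six-month window. This review does not choose between the two.

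The cost is a wording amendment to 5.2 and a check of a form already in use. If the rule in 2.3.1 is the one carried over, nobody is turned away whom the protocol does not already say is excluded. No procedure, visit or analysis changes.
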